**Table 3: Research Blood**

Test/assay	Volume blood (approx.)	Type of tube	Collection point (+/- 48hrs)	Location of specimen analysis
Immunemonitoring	48 mls (baseline) 48 mls (week 6)	6 Sodium heparin	Baseline, Week 6	ETIB Preclinical Core lab
PK (pre & post at week 2)	12 mls (4 draws)	Sodium heparin	Week 2	[name] lab
Flow cytometry for regulatory, naïve, memory and effector T cells	3 ml	1 EDTA	Baseline, Week 6	ETIB Preclinical Core lab
Immunophenotyping panel (CD3, CD4, CD8, B cells, and NK cells)	3ml	1 EDTA	Baseline, Week 6	Clinical Center CLIA certified lab
RNA sequencing	10ml	Sodium heparin	Week 6	Dermatology Branch

**Abbreviated Title:** Topical ruxolitinib in cGVHD

**Version Date:** 01/25/2021

#### 5.1.4 Machine learning imaging process

Through a collaboration with [name] at Vanderbilt University Medical Center, we will share de-identified clinical images of cGVHD skin lesions taken with both 2D and 3D cameras to build a repository necessary for training a machine to identify cutaneous cGVHD. The images will be used to determine a set of parameters and variations on optical assessments which collectively assess skin optical properties at an equivalent or superior level to subjective dermatologic exam.

### 5.2 SAMPLE STORAGE, TRACKING AND DISPOSITION

#### 5.2.1 ETIB Procedures

Blood and tissue samples, collected for the purpose of research under IRB-approved protocols will be stored and may be archived by the ETIB Preclinical Service, with the exception of blood samples for ruxolitinib analysis, which will be stored separately by the Blood Processing Core (BPC) until analysis. Any RNA or cDNA generated during the research process may be archived by the ETIB Preclinical Service. All data associated with archived clinical research samples is entered into the ETIB Preclinical Service's Microsoft Excel databases on frozen cells and plasma. These databases are stored on the NCI group drive in the ETIB Preclinical Service folder. Access to this folder is limited to ETIB clinical staff, requiring individual login and password. All staff in the Preclinical Service laboratory have received annually updated NIH/CIT training and maintain standards of computer security.

The data recorded for each sample includes the patient ID, name, trial name/protocol number, date drawn, treatment cycle/post-transplant time point, cell source (e. g. peripheral blood or skin biopsy) as well as box and freezer location. Patient demographics that correlate treatment outcomes and therapies with the samples can be obtained only through the NCI/ETIB clinical records or C3D. All samples currently receive a unique bar code number, which is included in the Preclinical Service Stored Sample database. Only this bar code will be recorded on the sample vial, and the vials will not be traceable back to patients without authorized access to the Preclinical Service database.

Samples are stored in locked freezers at -85°C (sera, plasma, RNA and cDNA) or under liquid nitrogen (cells), according to stability requirements. These freezers are located onsite at the ETIB Preclinical Service laboratory (12C216). Access to samples from a protocol for research purposes will be by permission of the Principal Investigator of that protocol or through his/her submission and IRB approval of the NIH IRB Authorization Form stipulating whether IRB review is not necessary or IRB approval is granted for the pursuit of this new research activity. All researchers are required to sign a form stating that the samples are only to be used for research purposes associated with objectives of the original protocol for which the samples were collected, or (using only unlinked or coded samples) for an IRB-approved protocol as stipulated on the IRB Authorization Form, and that any unused samples must be returned to the Preclinical Service laboratory.

##### 5.2.1.1 Protocol Completion/Sample Destruction

Once primary research objectives for the protocol are achieved, researchers can request access to remaining samples, providing they have both approval of the Principal Investigator of the original

*Abbreviated Title:* Topical ruxolitinib in cGVHD

*Version Date:* 01/25/2021

protocol under which the samples or data were collected and either an IRB-approved protocol and patient consent or the IRB Authorization Form stipulating that the activity is exempt from IRB review. Samples, and associated data, will be stored permanently unless the patient withdraws consent. If researchers have samples remaining once they have completed all studies associated with the protocol, they must be returned to the Preclinical Service laboratory.

If a patient withdraws consent, the participant's data will be excluded from future distributions, but data that have already been distributed for approved research use will not be able to be retrieved. The Preclinical Service staff will report to the Principal Investigators any destroyed samples, if samples become unsalvageable because of environmental factors (e.g., broken freezer or lack of dry ice in a shipping container), lost in transit between facilities or misplaced by a researcher. The Principal Investigators will annually report this information to the IRB. Freezer problems, lost samples or other problems associated with samples will also be reported to the IRB and the NIAMS Clinical Director.

### 5.2.2 Blood Processing Core

All samples sent to the Blood Processing Core (BPC) will be barcoded, with data entered and stored in the LABrador (aka LabSamples) utilized by the BPC. This is a secure program, with access to LABrador limited to defined [name] lab personnel, who are issued individual user accounts. Installation of LABrador is limited to computers specified by [name]. These computers all have a password restricted login screen. All [name] lab personnel with access to patient information annually complete the NIH online Protection of Human Subjects course.

LABrador creates a unique barcode ID for every sample and sample box, which cannot be traced back to patients without LABrador access. The data recorded for each sample includes the patient ID, name, trial name/protocol number, time drawn, cycle time point, dose, material type, as well as box and freezer location. Patient demographics associated with the clinical center patient number are provided in the system. For each sample, there are notes associated with the processing method (delay in sample processing, storage conditions on the ward, etc.).

#### 5.2.2.1 Sample Storage and Destruction

Barcoded samples are stored in barcoded boxes in a locked freezer at either -20 or -80°C according to stability requirements. These freezers are located onsite in the BPC and offsite at NCI Frederick Central Repository Services in Frederick, MD. Samples will be stored until requested by a researcher named on the protocol. All requests are monitored and tracked in LABrador. All researchers are required to sign a form stating that the samples are only to be used for research purposes associated with this trial (as per IRB approved protocol) and that any unused samples must be returned to the BPC.

Following completion of this study, samples will remain in storage as detailed above. Access to these samples will only be granted following IRB approval of an additional protocol, granting the rights to use the material.

Sample barcodes are linked to patient demographics and limited clinical information. This information will only be provided to investigators listed on this protocol, via registered use of the LABrador. It is critical that the sample remains linked to patient information such as race, age,

**Abbreviated Title:** Topical ruxolitinib in cGVHD

**Version Date:** 01/25/2021

dates of diagnosis and death, and histological information about the tumor, in order to correlate genotype with these variables.

If, at any time, a patient withdraws from the study and does not wish for their existing samples to be utilized, the individual must provide a written request. Following receipt of this request, the samples will be destroyed and reported as such to the IRB. The PI will report destroyed samples to the IRB if samples become unsalvageable because of environmental factors (ex. Broken freezer or lack of dry ice in a shipping container) or if a patient withdraws consent. Samples will also be reported as lost if they are lost in transit between facilities or misplaced by a researcher. Freezer problems, lost samples or other problems associated with samples will also be reported to the IRB and the NIAMS Clinical Director.

## **6 DATA COLLECTION AND EVALUATION**

### **6.1 DATA COLLECTION**

All data will be entered into C3D using predesigned CRFs. The PI will be responsible for overseeing entry of data into an in-house password protected electronic system and ensuring data accuracy, consistency and timeliness. Complete records will be maintained on each patient including the medical record with any supplementary information obtained from outside laboratories or physician's records. These records are the primary source documents that form the basis for the research record and will be uploaded in CRIS. The principal investigator, associate investigators/research nurses and/or a contracted data manager will assist with the data management efforts. All data obtained during the conduct of the protocol will be kept in secure network drives or in approved alternative sites that comply with NIH security standards. Primary and final analyzed data will have identifiers so that research data can be attributed to an individual human subject participant.

All adverse events, including clinically significant abnormal findings on laboratory evaluations, regardless of severity, will be followed until return to baseline or stabilization of event. Patients will be followed for adverse events for 30 days after removal from study treatment or until off-study, whichever comes first.

An abnormal laboratory value will be recorded in the database as an AE **only** if the laboratory abnormality is characterized by any of the following:

- Results in discontinuation from the study
- Is associated with clinical signs or symptoms
- Requires treatment or any other therapeutic intervention
- Is associated with death or another serious adverse event, including hospitalization.
- Is judged by the Investigator to be of significant clinical impact
- If any abnormal laboratory result is considered clinically significant, the investigator will provide details about the action taken with respect to the test drug and about the patient's outcome.

**End of study procedures:** Data will be stored according to HHS, FDA regulations, and NIH Intramural Records Retention Schedule as applicable.

**Abbreviated Title:** Topical ruxolitinib in cGVHD

**Version Date:** 01/25/2021

**Loss or destruction of data:** Should we become aware that a major breach in our plan to protect subject confidentiality and trial data has occurred, the IRB will be notified.

#### 6.1.1 Adverse Events

Grade 1 adverse events will not be collected on this protocol.

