## 1 INTRODUCTION

### 1.1 STUDY OBJECTIVES

#### 1.1.1 Primary Objective:

- To determine the safety and tolerability of topical ruxolitinib 1.5% cream in patients with cutaneous cGVHD with epidermal involvement (non-sclerotic form)
- To determine the efficacy of topical ruxolitinib 1.5% cream in patients with cutaneous cGVHD with epidermal involvement (non-sclerotic form) by calculating the percent decline in surface area involvement: ruxolitinib treated site decline minus the placebo treated site decline

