## 8 STATISTICAL CONSIDERATIONS

### 8.1 STATISTICAL HYPOTHESES

#### 8.1.1 Primary efficacy endpoints:

The primary objectives are to determine the safety and tolerability as well as the efficacy of topical ruxolitinib 1.5% cream in patients with epidermal cGVHD.

The primary safety and tolerability endpoint will be counts of the grades of adverse events noted. The primary efficacy endpoint will be the percent change in the surface area of the target lesions for ruxolitinib-treated vs. placebo-treated lesions.

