#### **8.4.4 Safety Analyses**

Safety of the agent will be assessed by reporting the grade of adverse events noted in each patient, and reporting the fraction with grade 3 and grade 4 adverse events. Safety data will be presented in individual listings. Summaries will also be prepared. The safety data will consist of the reporting of all adverse events, vital signs, physical examination data, and appropriate laboratory safety data.

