### 11.1.2 Toxicity

Topical ruxolitinib has been evaluated in over 2350 subjects in at least 17 clinical studies in healthy volunteers and participants with psoriasis, atopic dermatitis, alopecia areata and vitiligo for a duration of 1-26 months.

There have been no treatment related deaths. To date, only one severe, and/or life-threatening treatment emergent adverse event (TEAE), dermatitis atopic, has been attributed to the study drug. All other SAEs were considered unlikely related or unrelated to study drug.

Other TEAEs that led to discontinuation of topical ruxolitinib include mild to moderate occurrences of application site irritation, a Grade 3 elevation in GGT, headache, fatigue, nausea, atopic dermatitis and hypertriglyceridemia.

In an ongoing study of atopic dermatitis, a total of 67 pediatric participants (aged 2 to 17 years) received ruxolitinib cream 0.5%, 1.5%, or 0.75% cream BID. No participant had a fatal TEAE, SAE, or TEAE leading to discontinuation of ruxolitinib cream.

Cutaneous AEs were seen with similar frequency for vehicle-treated lesions and active comparator treated lesions when compared with topical ruxolitinib treated lesions.

The most common AEs that were considered possibly related to the study drug include transient hypoesthesia, transient leukopenia and reticulocytosis, pruritus, upper respiratory infections, nasopharyngitis, headache, acne, dermatitis atopic, and transient application site irritation. All were considered mild to moderate and resolved with or without the need for concomitant medications.

Oral ruxolitinib is FDA approved for treatment of myelofibrosis and polycythemia vera in adults. The most common AEs with oral administration include thrombocytopenia, anemia, neutropenia, infection, nonmelanoma skin cancer, elevation of AST and ALT. Systemic exposure with topical ruxolitinib is several fold below the doses that are associated with AEs following oral dosing.

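### Section 6.1.1 excludes grade 1 adverse events, which conflicts with Section 8.4.4 and gives the primary tolerability counts a grade 2 floor that Section 8 does not state

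*Combined protocol and SAP*

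**What the plan says.** Safety and tolerability comes first among the primary objectives in Section 1.1.1: "To determine the safety and tolerability of topical ruxolitinib 1.5% cream in patients with cutaneous cGVHD". Section 8.1.1 turns this into an endpoint: "The primary safety and tolerability endpoint will be counts of the grades of adverse events noted".

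Section 8.4.4 describes the analysis. It reports each patient's adverse event grades, and the only proportion it names comes from "reporting the fraction with grade 3 and grade 4 adverse events". It then defines the data: "The safety data will consist of the reporting of all adverse events, vital signs, physical examination data, and appropriate laboratory safety data".

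Section 6.1.1 consists of one sentence, with no exception and no reason given: "Grade 1 adverse events will not be collected on this protocol".

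Two other places bear on what is recorded. Section 6.1 has adverse events of every severity followed until they resolve or stabilise. Table 1 in Section 3.3 lists skin ulceration at a treatment site, at any grade, as a trigger for action.

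On the events to expect, Section 11.1.2 lists the commonest possibly related ones, pruritus and transient application site irritation among them, and adds: "All were considered mild to moderate and resolved with or without the need for concomitant medications". It also says of earlier studies: "Other TEAEs that led to discontinuation of topical ruxolitinib include mild to moderate occurrences of application site irritation".

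**The concern.** A collection rule and a reporting rule in the same document cannot both be followed. An event that is never collected cannot be listed or counted, so the floor in 6.1.1 decides what the primary tolerability endpoint can show.

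The events lost are of a kind the protocol itself expects. For a cream, tolerability is largely a matter of irritation, itch and similar reactions where it is applied. If mild corresponds to grade 1 (the documents do not map the terms, so this is an assumption), some of those reactions fall below the floor. A patient could then ask to stop treatment, as Section 3.8.1 allows, because of a reaction that never appears in the adverse event counts. A reader of the final report could take a short list of local reactions as good tolerability, when the list could only ever hold grade 2 and higher.

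**Working it through.** The plan gives no adverse event rate or precision target, so there is no figure of its own to reproduce on this point. The efficacy sample size does not depend on it.

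**The passages side by side**

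| Section | Lower grade limit | Consistent with 6.1.1? |
|---|---|---|
| 6.1.1, collection | Grade 2 | It is the rule |
| 8.1.1, primary counts | None stated; counts events noted | Only if noted means collected |
| 8.4.4, grade reporting | None stated; again events noted | Only if noted means collected |
| 8.4.4, content of safety data | None; every adverse event | No |
| 6.1, follow-up | None; every severity | Concerns follow-up, but implies a record |
| Table 1, treatment-site ulceration | None; any grade | Concerns action, but a grade 1 event would not be collected |

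The plain contradiction is between 6.1.1 and the content sentence of 8.4.4. Sections 6.1 and Table 1 conflict with 6.1.1 only over recording. I take no position on the action in the Table 1 row.

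**Illustration of the possible loss (assumed rates)**

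Inputs:
- n = 15, the accrual ceiling in Section 8.2. Section 6.3.1 makes all patients evaluable for toxicity from first treatment.
- p = share of patients with a local reaction of any grade. Assumed 10%, 20% or 30%.
- s = share of those patients whose reactions are grade 1 only. Assumed 0, 25%, 50% or 75%; s = 0 is equivalent to collecting all grades.

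Probability that no local reaction is recorded = (1 − p(1 − s))^15, taking patients as independent.

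| p | s = 0 | s = 25% | s = 50% | s = 75% |
|---|---|---|---|---|
| 10% | 20.6% | 31.1% | 46.3% | 68.4% |
| 20% | 3.5% | 8.7% | 20.6% | 46.3% |
| 30% | 0.5% | 2.2% | 8.7% | 31.1% |

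For example, p = 20% and s = 50% give (1 − 0.20 × 0.50)^15 = 0.90^15 = 20.6%, against 0.80^15 = 3.5% with all grades collected. At p = 20%, the expected number of patients recorded is 15 × 0.20 × (1 − s) = 3.0, 2.25, 1.5 or 0.75.

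If no reaction were recorded in 15 patients, the one-sided 95% upper bound would be 1 − 0.05^(1/15) = 18.1%. Under 6.1.1 that bounds the rate of grade 2 and higher reactions. It puts no bound on the any-grade rate.

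**Why a by-site comparison should stay descriptive**

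An exact two-sided sign test on patients who react at one site only needs 6 of 6 in the same direction: 2 × 0.5^6 = 0.031, while 5 of 5 gives 2 × 0.5^5 = 0.0625. Even if every reaction were on the ruxolitinib site, the chance of 6 or more in 15 patients is 0.2%, 6.1% or 27.8% for p = 10%, 20% or 30%.

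**The case against.** Several points on the other side stand.

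- **The floor looks deliberate.** Table 1 uses grade 1 or baseline as the level to which most events must resolve, the DLT definition in Section 3.1.1 does the same for brief grade 3 toxicities, and dry skin of any grade is exempt from dose modification. This is a fair reason not to collect every grade 1 event. It does not explain the any-grade ulceration row, and it does not bring 8.4.4 into line.
- **Local effects are captured elsewhere.** Section 3.4 takes pruritus and skin pain VAS separately for each site, and the Appendix G diary has columns for irritation, itching, pain and the reason for a missed dose. These cover part of the gap. They are not graded adverse events and do not enter the counts that define the endpoint.
- **Attribution is hard.** Both sites carry active epidermal cGVHD, with erythema, papules or scale, and Section 3.1 calls the disease waxing and waning. Mild redness or itch may be disease. This is a real drawback of collecting more, and it limits the fix.
- **The sites may not differ.** Section 11.1.2 reports similar cutaneous event frequencies on vehicle, active comparator and ruxolitinib lesions. That comes from other populations and does not remove the conflict over recording.

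Two stronger readings are tempting. A reader might infer that the limit is concealed. It is not: it has its own heading in the same document, and the word noted in 8.1.1 can be read as collected. The fault is that Section 8 does not carry the limit over.

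A reader might also take the statement in Section 11.1.2 that "only one severe, and/or life-threatening treatment emergent adverse event (TEAE), dermatitis atopic, has been attributed to the study drug", in over 2350 subjects, to mean that grade 3 and 4 events will hardly occur here. The text does not support that. The next sentence speaks of all other SAEs, so the figure appears to describe serious events. It covers attributed events only, whereas the proportion in 8.4.4 is not so limited. It comes from healthy volunteers and other diseases, and a separate grade 3 GGT elevation shows that it is not a count of grade 3 and 4 events.

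**Conclusion.** The concern holds as a conflict over what is collected and reported for a primary endpoint. With 6.1.1 in force, the tolerability counts are counts of grade 2 and higher, the content sentence of 8.4.4 cannot be met, and a grade 1 treatment-site ulceration would not be collected as an adverse event.

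That the counts may understate local reactions is a reasonable expectation from Section 11.1.2, but its size is unknown. The documents give neither reaction rates nor a split between mild and moderate, and equating mild with grade 1 is an assumption. The tables above show how the loss would behave and do not estimate it.

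Grade 2 and higher events are still collected. The grade 3 and 4 proportion, the DLT rule and the efficacy power are unaffected. The point should be fixed because it concerns a named primary objective and the repair is small.

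**What to change.** 1. Amend 6.1.1 so that application-site events of any grade that are new or worse than baseline are collected at either treated site, while other grade 1 events stay uncollected. Record them as Site 1 or Site 2, the labels already in Appendix F, so that the blind is kept. Map them to ruxolitinib or vehicle after unblinding. The adverse event assessments already scheduled every 2 weeks are enough.
2. Restate 8.1.1, 8.4.4 and 6.1 as grade 2 and higher, plus application-site events of any grade. This also closes the recording gap for the ulceration row of Table 1.
3. Report the number of patients with application-site events by grade and treated site, descriptively and without a test.

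If the sponsor prefers to keep the full exclusion, the minimum is to state the grade 2 floor in 8.1.1 and 8.4.4, limit the tolerability conclusion to grade 2 and higher, and reconcile 6.1 and the any-grade ulceration row as to recording.

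The cost is an amended sentence in 6.1.1, matching wording in three sections, and one line per site on the adverse event form for at most 15 patients over 6 weeks of treatment. The drawbacks are slightly more data entry and some recorded events that are really cGVHD activity. The baseline comparison reduces the second problem but does not remove it, so the vehicle site serves only as a descriptive within-patient comparator.
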